12.3 Device Deficiencies

Investigators are instructed to report all possible device deficiencies, malfunctions, misuse or use error observed during the trial. These incidents will be documented in the case report form provided as follows:

Device deficiency: Inadequacy in the identity, quality, durability, safety, or performance
of an investigational medical device, including malfunction, use errors or inadequacy in
information supplied to the manufacturer. NOTE 1: Device deficiencies include
malfunctions, use errors, and inadequacy in the information supplied by the manufacturer
including labeling. They may or may not affect device performance or lead to an adverse

event. NOTE 2: This definition includes device deficiencies related to the investigational medical device or the comparator.

- Device malfunction: Failure of an investigational medical device to perform in accordance with its intended purpose when used in accordance with the Instructions for Use or protocol. NOTE: A device malfunction occurs when the device is used in compliance with the Instructions for Use but does not perform as described in the Instructions for Use.
- Use error: Act or omission of an act that results in a different medical device response than intended by the manufacturer or expected by the user. NOTE 1: Use error includes slips, lapses and mistakes. NOTE 2: An unexpected physiological response of the subject does not itself constitute a use error.
- Device misuse: Any use of the investigational device by an investigator that is contradictory to the application described in the Instructions for Use will be categorized as device misuse. This is a form of Use Error.

Investigators shall report Device Deficiencies as follows:

- All sections of the Device Deficiency eCRF shall be completed for each DD related to the investigational medical device or the comparator device.
- Assess and report if the device deficiency could have led to a serious adverse device effect:
 - o If either suitable action had not been taken,
 - o If intervention had not been made, or
 - If circumstances had been less fortunate
- If an adverse event results from a device deficiency it should be reported on an Adverse Event eCRF
- If possible, the investigational device should be returned to Conformal Medical for analysis. See the Manual of Procedures for device returns.

Following completion of the subject's 18 Month follow-up, adverse event collection will be limited to the following:

- All serious adverse events
- All device deficiencies
- Unanticipated adverse device effects
- All adverse events of special interest, regardless of seriousness, as defined above

12.4 Unanticipated (Serious) Adverse Device Effect (UADE/USADE)

Investigators (or designee) must report any potential unanticipated (serious) adverse device effects to the Sponsor (or Sponsor's representative) and their IRB/REB/EC as soon as possible but no later than within 1 business days after the investigator first learns of the event. Potential UADEs should be reported immediately on the eCRF and to the Sponsor (telephone, email, other). Guidelines of how to report potential UADEs are listed in the Study Manual of Procedures.

If an event is determined by Conformal Medical to be a UADE, the Sponsor will report the event to the FDA and other applicable regulatory authorities as well as all participating IRB/ REB/ECs (or other, as required) and all investigators.

12.5 Serious Health Threat (SHT)

Per ISO 14155:2020, a serious health threat is a signal from any adverse event or device deficiency that indicates an imminent risk of death or a serious deterioration in the health in subjects, users or other persons, and that requires prompt remedial action for other subjects, users or other persons.

NOTE 1: This would include events that are of significant and unexpected nature such that they become alarming as a potential serious health hazard or possibility of multiple deaths occurring at short intervals.

12.6 Safety Event Reporting Timelines for Investigational Sites

Event	Timeline to Report to Conformal Medical	How to Report
Adverse Event (AE) / Adverse Device Effect (ADE)	Within 10 business days, or as soon as is feasibly possible upon awareness of the event	eCRF
Serious Adverse Event (SAE) / Serious Adverse Device Effect (SADE)	Within 2 business days of awareness of the event	eCRF
Unanticipated Adverse Device Effect (UADE) / Unanticipated Adverse Device Effect (USADE)	Within 2 business day of awareness of the event	email to sponsor
Device Deficiency	Within 2 business days of awareness of the event	eCRF

NOTE: If the eCRF is not available, the site should notify the Sponsor via email within the associated timeline(s) above based on date of awareness of event.

Email Notification: [contact]

The email should include the Subject ID, date of awareness of the event, date of onset of symptoms, the AE term, the seriousness, the relatedness to the investigational device and/or procedure, any actions taken, and the outcome, if known.

12.7 Expected Adverse Events – Risk/Benefit Analysis

The device and procedure are both associated with risks. Below is a summary of the expected risks that may occur. They are divided between those events associated with the procedure versus those associated with the CLAAS system. There may be additional risks that are unknown at this time. Risks associated with concomitant medications related to LAAO index procedure may be outlined in the informed consent form, if required by local IRB/REB/EC or equivalent.

12.7.1 Procedural Risks: The risks of delivery of the CLAAS device are like those of other procedures that require a transseptal puncture, TEE and transcatheter delivery of an implant through the venous system, across the interatrial septum, and into the left atrium using a large bore catheter (e.g., EP procedures and/or other LAA devices such as WATCHMAN and Amulet).

These risks are well recognized and experienced clinicians that are well versed in the use of large bore catheters have mitigated these risks to the extent possible in their standard of care. The recognized procedural risks observed in prior studies with CLAAS and other LAAO products include (in alphabetical order):

- Acute Kidney Injury potentially requiring need for dialysis
- Air embolus
- Allergic reaction to contrast media necessary for imaging during procedure
- Anesthesia risks (e.g., nausea/vomiting, aspiration pneumonia)
- Arrhythmia
- Bleeding/anemia requiring transfusion
- Cardiac Perforation, Puncture, Tamponade, and/or Effusion requiring drainage and/or "open heart" surgery
- Chest pain/angina
- Damage to cardiac structure (e.g., valve, chordae)
- Death
- Deep Vein Thrombosis or Pulmonary Embolism
- Dyspnea
- Electrolyte imbalance
- Fever
- Heart Failure
- Hematuria
- Hemodynamic Instability (hypotension/hypertension)
- Hemothorax
- latrogenic ASD requiring treatment
- MI including ST segment elevation
- Pericardial Effusion/tamponade
- Pleural Effusion
- Pulmonary Edema
- Respiratory failure
- Stroke/TIA or Systemic embolization
- Systemic Infection including pneumonia
- TEE/intubation risks including throat pain, trauma to airway or esophagus with or without bleeding
- Thrombocytopenia
- Thromboembolic event

• Venous access site complications including pain, AV fistula, pseudoaneurysm, infection, hematoma, bleeding requiring transfusion and/or the need for surgical repair

12.7.2 Device Risks: In addition to the risks of undergoing an interventional procedure, there should be consideration to the risks which are specific to the CLAAS Implant and CLAAS Delivery System. Conformal Medical has identified a set of risks that the rates of which may be different due to the design of the CLAAS system as outlined below. A number of the risks have been determined to be present with other interventional (e.g., WATCHMAN or Amulet) as well as surgical implants designed to occlude the LAA. These risks include but are not limited to:

- Arrhythmias
- Cardiac perforation, puncture, tamponade, and/or effusion caused by device
- Chest pain
- Deep Vein Thrombosis or Pulmonary Embolism
- Death
- Device embolization or thrombosis
- Device malfunction/breakage resulting in the inability to reposition, recapture or retrieve requiring further intervention
- Device manipulation resulting in the inability to reposition, recapture or retrieve requiring further intervention
- Device migration requiring intervention
- Infection
- Heart Failure
- Major bleed requiring transfusion
- Myocardial Erosion
- Prolonged procedure time risk
- Re-intervention due to incomplete seal
- Re-intervention to remove device
- Residual leak in LAA
- Stroke/TIA or Systemic embolization
- Thrombus formation

12.8 Methods to Minimize Risks

Extensive risk management activities have been conducted during the development of the CLAAS System to identify and analyze known and foreseeable hazards and reasonably foreseeable sequences or combinations of events that could result from using this product and the risks associated with each hazard. Mitigations have been implemented in the design, processes, and/or labeling and Instructions for Use of the product to reduce the residual risk of each hazard to levels that are as low as reasonably practicable.

The clinical investigational plan is specifically designed to manage and minimize risks through the selection of qualified and experienced investigators, thorough training of investigators and the investigational team, careful subject selection, adherence to pre-determined time points to assess

subject clinical status, and regular clinical monitoring visits by Sponsor-appointed monitoring personnel. In addition, an independent Data Safety Monitoring Board will review accumulating safety data at regular intervals to monitor for the incidence of serious adverse events that would warrant modification or termination of the trial. Also, an independent Clinical Events Committee will meet regularly to adjudicate the relationship of site-reported adverse events to the investigational device and procedure.

12.9 Potential Benefits

The targeted subject population consists of patients presenting with non-valvular atrial fibrillation, and who are at increased risk for stroke and systemic embolism and are recommended for OAC therapy but have an appropriate rationale to seek a non-pharmacological alternative to OAC, and who have been deemed appropriate for LAA closure by the Site PI and a physician not on the interventional team or an advanced provider using a shared decision-making process. Compared with LAA closure with a commercially available device, LAA closure with the CLAAS System may offer a simpler, safer implantation procedure and an increased likelihood of achieving successful closure.

Subjects in the CONFORM Pivotal Trial may not derive any direct benefit from their participation in the trial; however, subjects may gain satisfaction from having made an altruistic contribution to medical science, and the results of the trial may contribute to improved treatments that could benefit future patients who require LAA occlusion for the prevention of stroke and systemic embolism.

12.10 Benefit-Risk Assessment

A risk analysis of the CLAAS System has been performed and concluded that the identified risks have been reduced to a level as low as reasonably practicable. When combined with the risk management measures incorporated into the design of the clinical trial, the potential benefits of the clinical use of the CLAAS System in the CONFORM Pivotal Trial are judged to justify the potential risks to study participants. The potential benefits and risks of study participation will be evaluated on an individual basis and discussed with each subject prior to enrollment in the study.

This clinical investigation has been designed to comply with the requirements of EU MDR Chapter VI, Article 62 4(i), including the monitoring of risk as detailed in section 12.1.10.

13 Study Committees and Safety Oversight

13.1 Executive Committee

The Executive Committee will be comprised, at a minimum, of the Principal Investigators, one or more representatives from the Imaging Core Labs, and one or more Sponsor Representatives. The Executive Committee will be responsible for scientific and operational management of the trial and will meet regularly prior to and during the trial to monitor trial progress and make recommendations related to potential modifications/enhancements to the investigational plan.

13.2 Clinical Events Committee (CEC)

An independent Clinical Events Committee (CEC) will adjudicate all site-reported potential endpoint events and any other events the Sponsor deems necessary, in an ongoing fashion during the trial. Relationship of these events to the assigned device and/or procedure will also be adjudicated, and sub-classified as implant-related, delivery system-related or study medication related (anti-coagulation or antithrombotic) or related to a comorbid condition. The committee will include at least three voting members consisting of qualified physicians (cardiologists, interventional cardiologists, electrophysiologists and/or neurologist) experienced in clinical trials who are otherwise independent of the Sponsor and the conduct of the study. Members will also

be selected with consideration of their experience in the conduct of clinical trials and prior participation on a Clinical Events Committee.

Members will not have scientific, financial, or other conflicts of interest related to Conformal Medical, Inc. or the Investigator(s). The CEC will operate and conduct all meetings and event reviews independent of the Sponsor unless specific expert knowledge regarding the characteristics or function of the study device is requested by the CEC from the Sponsor.

The adjudication process, event definitions and required source document materials for each type of event will be pre-specified prior to the onset of the trial. The CEC members will review data collected from all relevant medical records, as well as all imaging study reports associated with an event to perform adjudication. All adjudication decisions will be made by the CEC in an independent and blinded fashion (to the extent possible) based upon review of all available medical evidence. Treatment assignment to investigational device/control device will be deidentified in any source documentation reviewed by the CEC to maintain blinding and reduce any potential bias.

13.3 Data Safety Monitoring Board (DSMB)

An independent Data Safety Monitoring Board (DSMB) will be responsible for the oversight and safety monitoring of the study. The DSMB will advise the Sponsor regarding the continuing safety of the trial subjects and those yet to be recruited to the trial, as well as the continuing validity and scientific merit of the trial. The DSMB will include qualified cardiovascular trained physicians and a biostatistician with expertise in the study procedure and in clinical trials who are otherwise independent of the Sponsor and the conduct of the study, and do not have scientific, financial or other conflicts of interest related to Conformal Medical, Inc. or the Investigator(s).

During the enrollment phase of the trial, the DSMB will review accumulating safety data at regular intervals to monitor for the incidence of serious adverse events that would warrant modification or termination of the trial.

Any DSMB recommendations for study modification or termination prompted by concerns regarding subject safety or issues relating to data monitoring or quality control will be submitted in writing to the Sponsor for consideration and final decision. However, if the DSMB, at any time, determines that a potential serious risk exists to subjects in this trial, the DSMB will immediately notify the Sponsor.

DSMB responsibilities, personnel, procedures, and data review content and frequency will be outlined in the DSMB Charter.

13.4 Core Laboratories

Independent Imaging Core Laboratories will be utilized to analyze echocardiogram and CT imaging during the trial. Echocardiograms performed during and after the implant procedure and CT performed at 12-M follow-up; or at the request of Conformal, will be de-identified and reviewed by the Core Labs. Members of the Core Lab will have no affiliation with the CONFORM Pivotal Trial. The Manual of Procedures provides all Core Lab instructions for image acquisition as well as image uploading.

14 Statistical Considerations and Analysis Plan

Key statistical information is provided below. Additional details, including plans for handling missing data, poolability, subgroup analyses, and sensitivity analyses are outlined in a separate standalone Statistical Analysis Plan.

14.1 Sample Size Rationale

14.1.1 Effectiveness Endpoint

The sample size is driven by the power requirements for the primary effectiveness endpoint and was determined via simulation.

The 18-month study endpoint is defined as the composite of ischemic stroke or systemic embolism through 18 months. The estimated event rate used for power calculations is 4.14%. The estimated rate has been derived from the reported rate for WATCHMAN FLX through 12 months and Amulet through 18 months as described below.

The 12-month CEC-adjudicated major clinical event rates of 2.6% and 0.3% were reported for ischemic stroke and systemic embolism respectively (21) for WATCHMAN-FLX, which is the most prevalent product in use). The values of 2.6% and 0.3% were summed to produce a 12-month estimated rate of 2.9%. A linearized rate over the time from between 12 and 18 months was calculated to arrive at the final estimated anticipated rate of 4.4%. This reflects a 50% increase in the event rate from 12 to 18 months. For Amulet, the reported rate of ischemic stroke and systemic embolism was reported as 2.8% at 18 months. (26)

It is anticipated that the enrollment of control cases in CONFORM, will comprise approximately 80% WATCMAN-FLX cases and approximately 20% of Amulet cases. Using a weighted average of event rates based on this composition yields an overall estimated rate of 4.1%.

With a non-inferiority margin of 3.2%, and one-sided alpha level of 0.025 the sample size of up to 1600 subjects should provide greater than 85% power for the hypothesis test of non-inferiority accounting for a 10% attrition rate.

A non-inferiority margin of 3.2% is reasonable given precedent of similarly sized margins in previous studies, the expected underlying event rates, and power requirements for the study. For an expected event rate of 4.1%, a 3.2% margin corresponds to a relative increase of 78%.

14.1.2 Safety Endpoint

The planned sample size is expected to provide sufficient power for the hypothesis test for the primary safety endpoint. Specifically, assuming an underlying safety event rate in both groups of 15% (similar to those reported for the Amulet study (26) with a 5.8% non-inferiority margin, a total of approximately 1200 subjects would provide greater than 80% power based on an un-pooled ztest at the one-sided 0.025 alpha level. Given the larger sample size required for the primary effectiveness endpoint, this approximation should be reasonable, and the planned sample size provide a high degree of power. A margin of 5.8% is approximately 38% of the value of the expected rate, reflecting a clinically reasonable non-inferiority margin given the underlying expected event rate.

14.2 Analysis Populations

Section 8.8 describes the different subject classifications in the study. The ITT Randomized population will be used to analyze the Primary Safety and Efficacy Endpoints. Additional analyses of different populations (Attempted and Implanted) will be considered supportive in nature for the Primary Safety and Efficacy Endpoints and will the utilized to examine other Secondary Endpoints. Additional analyses of populations who receive the Initial CLAAS System vs. the Next Generation CLAAS System will be performed.

14.3 Method of Analysis & Reporting

All endpoints will be reported using appropriate descriptive statistics. Statistics for continuous variables will include sample size, mean, standard deviation, median, interquartile range,

minimum, and maximum. Binary variables will be summarized using sample size, frequencies, and percentages.

Analysis will be conducted using SAS (version 9.4 or greater), unless otherwise noted. Additional details will be pre-specified in the formal Statistical Analysis Plan (SAP).

14.4 Baseline Characteristics

The following data will be summarized using descriptive statistics and presented:

- Baseline demographics
- Baseline comorbidities, risk factors, and medical and surgical history, including NYHA and
 if applicable, anginal status (may be done per standard of care up to 30 days prior to
 consent)
- Cardiac risk factors and cardiac history
- Procedural characteristics
- Device details

14.5 Study Hypothesis

14.5.1 Primary Effectiveness

The primary effectiveness endpoint will be assessed with the following non-inferiority hypothesis:

 H_0 : Pt - Pc ≥ 0.032 H_A : Pt - Pc ≤ 0.032

where Pt and Pc are the proportion of subjects with primary effectiveness endpoints in the treatment and control groups respectively at 18 months (study day 547) and 0.032 represents the non-inferiority margin. The hypothesis will be evaluated using a one-sided 97.5% confidence interval for the difference in event rates based on the Kaplan-Meier estimate based on a linear transformation. If the one-sided upper confidence bound for the difference is less than the non-inferiority margin, the objective will be met, and the treatment group will be non-inferior to the control group for the primary effectiveness endpoint.

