NOTE: If the subject has not yet been discharged from the index procedure hospitalization at day 7 post-procedure, the 7-day follow-up may be conducted in-hospital.

Statistical Summary

All endpoints will be reported using appropriate descriptive statistics. Statistics for continuous variables will include sample size, mean, standard deviation, median, interquartile range, minimum, and maximum. Binary variables will be summarized using sample size, frequencies, and percentages. Kaplan-Meier analysis will be used for time-to-event analyses.

The primary effectiveness endpoint will be analyzed for non-inferiority based on a margin of 0.032. The primary safety endpoint will be analyzed for non-inferiority based on a margin of 0.058. The primary effectiveness and safety endpoints will also be reported using descriptive statistics and nominal confidence bounds.

Safety Oversight The will include subject safety protection measures that include safety committees that will assure patient safety. The study will include an independent Clinical Events Committee comprised of a multi-disciplinary team of physicians that will adjudicate all SAFETY ENDPOINT events and confirm causality and seriousness. An independent, multi-disciplinary Data Safety Monitoring Board will also be established and is tasked with reviewing all safety data at regular intervals to monitor for the incidence of serious adverse events that would warrant modification or termination of the trial. Public Release of The CONFORM TRIAL (Roll-In and Pivotal Trial Phase) is listed on clinicaltrials.gov under NCT05147782. Study and Results The CONFORM TRIAL (Conscious Sedation Sub-Study) is listed on clinicaltrials.gov under separate NCT06049615. In accordance with the requirements of ClinicalTrials.gov (as outlined Section 801 of the FDA Amendments Act) results will be posted when the complete data analysis is performed.

5 Study Schedule of Assessments

	Screening	Procedure ⁰	Pre- Discharge	7-Day	45-Day	6 Month (180 days)	12 Month (365 days)	18 Month (545 days)	2, 3, 4, 5 Year (730, 1095, 1460, 1825 days)	Stroke/SE Assessment ¹
		Day 0		+2 Days	±7 Days	±30 Days	±30 Days	±30 Days	±60 Days	+14 Days
	Clinic Visit			Telehealth ²	Clinic Visit/ Telehealth ²	Telehealth ²	Clinic Visit/ Telehealth ²	Clinic Visit	Telehealth ²	
Informed Consent	Х									
Medical and Surgical History	Х									Х
Physical Exam/Assessment	Х									Х
Vital Signs	Х									
CHA ₂ DS ₂ -VASc	Х									
HAS-BLED	Х									

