8.5.2 Primary Effectiveness Endpoint

The primary effectiveness endpoint is a composite of ischemic stroke (NeuroARC (29) defined) and systemic embolism through 18 months.

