8.8.4 Attempted Population

The Attempted Population includes all ITT subjects in whom a LAAO procedure has been attempted, i.e., the LAAO access sheath was inserted into the body.

The Attempted Population includes two groups: 1) subjects who undergo LAAO Procedure and receive a LAAO Closure Device and 2) subjects in whom a undergo the procedure without receiving a LAAO device.

Following index procedure hospitalization discharge, these subjects in the Attempted Population who do NOT receive an implant will not be required to have subsequent protocol mandated imaging and will not be required to follow the medication requirements. Subjects who do not receive an implant must be followed through the Primary Safety and Efficacy Endpoints with telehealth/phone call visits (at all visits including 7-days, 45-days, 6-months, 12-months, and 18-months) assessing only: QVSFS, AE Assessment, and Concomitant Medication Assessment. If a subject in the Attempted Population group experiences a suspected stroke or systemic embolism, that subject should be brought in for an Unscheduled Visit (in-person clinic visit) for assessment per the Schedule of Assessments matrix. After the 18-Month visit, these subjects will have completed all required study assessments.

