9.12 Eighteen-month Follow-up ± 30 Days (Clinic Visit)

All subjects will complete a clinical assessment at 18 months (± 30 days) post-procedure with an in-person clinical visit to complete the Primary Endpoint Assessment. The 18-month follow-up visit will include the following assessments:

- Neurological assessment may be performed by a non-delegated neurology professional (e.g., board-certified or board-eligible neurologist, neurology fellow, neurology physician assistant, or neurology nurse practitioner, or NIHSS- and/or mRS-certified staff where applicable), as long as assessments are completed as part of standard of care and documentation of current certification is maintained in site Regulatory files.:
 - Questionnaire for Verifying Stroke-Free Status (QVSFS) If any question is answered "Yes," a formal neurologic examination and evaluation must be performed by a board-certified neurologist or clinical designee (e.g., neurology fellow).
 - NIH Stroke Scale (NIHSS).
 - Modified Rankin Scale (mRS) to establish the disability or dependence in the daily activities of people who have suffered a stroke or other causes of neurological disability at baseline.
- Current concomitant medications documentation.
- Adverse event assessment.

Prior to concluding the visit, research staff should also review the follow-up requirements with the subject to help ensure continued study compliance.

NOTE: Subjects who had a procedure attempt but did not receive an implant must be followed through the Primary Endpoints with a minimum of telehealth/phone call visits at all visits including 7-days, 45-days, 6-months, 12-months, and 18-months (imaging not required and protocol mandated medication therapy not required). After the 18-Month follow-up, these subjects will have completed all required study assessments.

9.13 Annual Follow-up 2 – 5 Years ± 60 Days Post Index Procedure (Telehealth)

All subjects will complete annual telehealth visits (at a minimum) at 2, 3, 4 and 5-years (± 60 days) post-index procedure to include the following assessments:

- Questionnaire for Verifying Stroke Free Status (QVSFS) If any question is answered "Yes," a formal neurologic examination and evaluation must be performed by a board-certified neurologist or clinical designee (e.g., neurology fellow).
- Current concomitant medications documentation.
- Adverse event assessment.

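### A compliant 18-month visit can fall up to 32 days before the day-547 effectiveness landmark, and subjects without an implant leave the study at that visit

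*Protocol*

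**What the plan says.** The primary effectiveness endpoint (Protocol 8.5.2) is a "composite of ischemic stroke (NeuroARC (29) defined) and systemic embolism through 18 months". Section 14.5.1 takes the proportions "respectively at 18 months (study day 547") and tests them with a "one-sided 97.5% confidence interval for the difference in event rates based on the Kaplan-Meier estimate based on a linear transformation".

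The Section 5 table counts from the procedure as day 0. It labels the visit "18 Month (545 days") and allows ±30 days. Section 9.12 repeats the window ("All subjects will complete a clinical assessment at 18 months (± 30 days) post-procedure") and states the purpose: an "in-person clinical visit to complete the Primary Endpoint Assessment".

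Three places release subjects without an implant at this contact:

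- Section 8.8.4 says of subjects with an attempted procedure and no implant: "After the 18-Month visit, these subjects will have completed all required study assessments".
- Section 8.8.3 has the same sentence for subjects who lose eligibility after randomisation.
- The note in 9.12 says the same for attempted procedures without an implant.

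Sections 8.8.3 and 8.8.4 also require these subjects to be followed through the primary safety and efficacy endpoints.

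For other subjects, 9.13 provides telehealth contacts at 2 to 5 years (±60 days) with the stroke-free questionnaire (QVSFS) and adverse event assessment. The end of 12.3 keeps serious events and events of special interest reportable after month 18, and 12.1 lists stroke and systemic embolism among the latter.

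**The concern.** An estimate at day 547 needs each subject's status known through day 547. The visit meant to settle that status can be held on schedule and still come too early. For a subject whose last required contact is that visit, the remaining days are never observed, although the subject missed nothing. Sections 8.8.3 and 8.8.4 then cannot both be met: a subject released on day 515 has not been followed through an endpoint read at day 547.

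These subjects belong to the ITT Randomized population used for the primary analysis (14.2). The tipping-point analysis in 14.8 treats censored subjects as having missing endpoint status. The schedule therefore creates missing data on the primary endpoint that a phone call would prevent.

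**Working it through.** **The plan's own power figure.** Inputs from 8.3.2, 14.1.1 and the 1:1 allocation: event rate 4.14% (taken as equal in both arms), margin 0.032, one-sided alpha 0.025, 1600 subjects, 10% attrition, so 1600 × 0.9 / 2 = 720 per arm.

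- SE = √(2 × 0.0414 × 0.9586 / 720) = 0.0105
- Power = Φ(0.032 / 0.0105 − 1.96) = 86.2%

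This agrees with the stated power of about 85% or more.

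**The gap.**

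- Earliest compliant visit: 545 − 30 = day 515. Gap to the landmark: 547 − 515 = 32 days.
- Visit on target: 547 − 545 = 2 days short.
- Section 14.5.1 does not state the origin of study day. If it is randomisation, which may precede the procedure by up to 14 days (9.4), the largest gap is between 32 − 14 = 18 and 32 days.

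**Who can be covered later.**

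- Subjects with an implant: the 2-year contact falls on days 670 to 790 and can cover days 515 to 547.
- Subjects without an implant: no required contact follows. Section 9.13 is worded for all subjects, but the specific rules in 8.8.3, 8.8.4 and the 9.12 note end their assessments at 18 months.
- The 12-month safety endpoint does not share the problem. Its landmark and visit target are both day 365, and the 18-month contact (days 515 to 575) covers an early 12-month visit in both groups.

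**Share seen early (assumption: visit days spread evenly over days 515 to 575).** 32 of 61 possible days precede day 547, or 52%, with a mean shortfall of (1 + 32) / 2 = 16.5 days.

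**Events in the gap (assumption: constant hazard).** h = −ln(1 − 0.0414) / 547 = 0.0000773 per day.

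- All subjects last seen on day 515: exp(−515h) − exp(−547h) = 0.24 percentage points, or 720 × 0.0024 ≈ 1.7 events per arm.
- All subjects last seen at an evenly spread visit: 720 × 0.52 × 16.5 × 0.0000773 ≈ 0.5 events per arm.

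**Effect on power.** Greenwood variance, S(547)² × ∫ h / (S·G) dt / 800, with 800 per arm and 10% exponential attrition by day 547. Here S is the event-free curve and G the probability of remaining uncensored.

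| Who is censored at the 18-month visit | Power |
|---|---|
| Nobody | 87.9% |
| 5% to 20% of subjects, visits evenly spread | 87.8% to 87.7% |
| Every subject, visits evenly spread | 87.0% |
| 90% of subjects, all on day 515 (extreme) | 71% |

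The first row exceeds 86.2% because attrition is spread over time here, instead of removing 160 subjects at the start. The protocol does not give the number of subjects without an implant, so 5% to 20% is an assumed range.

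**The case against.** The strongest reply is that most subjects are not lost at all. Those with an implant remain under follow-up, stroke and embolism stay reportable, and 12.6 asks for serious events within 2 business days of awareness, whatever the visit date. Kaplan-Meier accommodates the remaining censoring, the effect should be similar in both arms, and the tipping-point analysis in 14.8 is a sensitivity analysis that leaves the primary estimate unchanged. Censoring rules and the data cut normally belong in the SAP. All of this stands, and it limits the point to subjects with no later contact.

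Two stronger readings are tempting and are not supported:

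- A reader might infer that about half the trial, 32/61 × 1440 ≈ 755 subjects, is censored before the landmark. That would follow only if each subject's data stopped at the 18-month visit, which the protocol does not say.
- A reader might take June 2028 in Table 4 as the primary read-out. The table gives it as the last subject's last efficacy follow-up and states no data-cut date. If data were cut then, with even enrolment over 54 months, roughly the last 4 to 8 months of enrolment would lack a 2-year contact. That is 4/54 to 8/54 × 1600 ≈ 119 to 237 subjects before attrition, about 62 to 124 of them seen early. This is an illustration and not a figure from the plan.

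What the reply does not remove is the exit rule. An SAP can choose a censoring date, but it cannot create observation time for a subject the protocol has released.

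Separately, 9.5.7 and the note in 9.9 end follow-up at 45 days for some subjects whom 8.8.3 follows to 18 months. That contradiction is larger and needs its own reconciliation.

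**Conclusion.** The point holds in a limited form. The protocol uses two day counts for 18 months, and a compliant visit can precede the effectiveness landmark by up to 32 days (18 to 32 if study day runs from randomisation). The gap is permanent for ITT subjects without an implant, and it applies at analysis to anyone without a later contact by the primary data cut.

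The size is small: less than 1 point of power even if every subject were censored at an evenly spread visit, and about half an expected event per arm in that case. Both figures rest on a constant hazard at the planned 4.14% rate and on visits spread evenly over the window. The reason to act is that the schedule produces avoidable missing status on the primary endpoint in subjects who complied fully, and that its exit rule contradicts its own follow-up requirement.

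**What to change.** - Use one day count for 18 months in the Section 5 table, 9.12 and 14.5.1, and state the origin of study day.
- In 8.8.3, 8.8.4 and the 9.12 note, do not let subjects without an implant complete the study before the landmark day.
- For any subject whose 18-month visit precedes the landmark and who has no later contact before the primary data cut, require the existing telehealth contact (QVSFS and adverse event assessment) on or after the landmark day.

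Moving the whole visit window to open at the landmark is a possible alternative, but it is not needed.

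The cost is a protocol amendment with the usual ethics review and a short extra phone contact for a minority of subjects. Last contacts may move by up to about a month. Visits already held cannot be moved, but with enrolment forecast to December 2026 many 18-month contacts are still to come.
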